7.5 Schedule of Events

Action	Enrollment	Interventional: Pre-operative Phase	Interventional: In-Patient Phase	Interventional: Long-Term Follow-up Phase
Consent	X			
Demographics	X			

Baseline Function Assessment	X			
Palliative Care Visit/Consult		X	X	X
Post-op phone call				X (~30, ~60, ~90 days after operation)
90 Day Post-op Assessment				X
180 Day Post-Op Assessment				X
Zarit Burden Interview				X
Biannual Assessments				X (~Every 6 months after 180 days evaluation)
Final Assessment				X

7.6 The Vanderbilt Coordinating Center (VCC). The VCC has extensive experience in the conduct of large, phase III clinical trials over the past decade. The VCC will perform (among other functions) the following: design the database and data collection tool, conduct site-training regarding protocol implementation and delirium monitoring to standardize all research activities during the trial, monitor enrollment pace and quality to ensure patients meet the inclusion/exclusion criteria, maintain blinding, track adverse events and ensure safety reporting, ensure protocol compliance, conduct follow-up phone testing of neuropsychological function and quality of life via neuropsychology technicians, and work with local study personnel using multiple proven patient retention techniques that have consistently achieved over 80% follow-up during previous studies.

8.0 Risks and Benefits of Mitigating Risks. Risks are minimal in this study. Some questions that are asked may be emotionally upsetting when noting that for example quality of life has declined or caregiver may be sad talking about their loved one that has died. The benefits of this study may have a great impact on patient outcomes, quality of life, and may have an impact on patients' likelihood to survive a life-threatening illness. During the consenting process and assessments, the research staff along with palliative care team will be mindful of patient's and caregiver's feelings and provide resources for them if appropriate such as counseling with a trained professional.

8.1 Data and Safety Monitoring Plan. To ensure data is accurately and completely collected during the SCOPE trial, the VCC will follow a specific Data Monitoring Plan. A VCC member will assure that the study protocol is being followed and that changes to the protocol have been approved by the local IRB. Also, the VCC will oversee that subject records are reviewed to determine whether data collected is accurate, complete, and current. Not only will the VCC be part of the Data and Safety Monitoring plan but it is also follows monitoring expectations set by the Vanderbilt-Ingram Cancer Center (VICC).

Purpose

VICC oversees patient safety and data monitoring for its investigator-initiated and NIH-NCI funded clinical trials through its Data and Safety Monitoring Committee (DSMC). The purpose of the DSMC is to ensure the efficient implementation and management of the VICC Data and Safety Monitoring Plan (DSMP). The Committee maintains authority to intervene in the conduct of studies as necessary to ensure clinical research performed at VICC achieves the highest quality standards.

Data and Safety Monitoring Plan

The VICC DSMP which is approved by the NCI Data and Safety Monitoring Review Panel, is accessible to all VICC investigators through the VICC website: <https://intranet.vicc.org/vu/dsmc/>

The plan addresses the following:

- Proper monitoring of trial progress and the safety of clinical trial participants
- Compliance with requirements regarding the reporting of adverse events as per institutional and federal guidelines
- Scope of temporary or permanent suspension of an NCI-funded trial
- Data accuracy and protocol compliance

Data and Safety Monitoring Committee

The VICC DSMC membership is listed on the VICC website: <https://intranet.vicc.org/vu/dsmc/>

Primary responsibilities of the VICC DSMC include the following:

- Review of serious adverse event reports for investigator-initiated and NCI funded studies and ensuring appropriate actions have occurred in response to these documents
- Audit institutional trials to ensure that the conduct and integrity of the trials are of the highest quality and that all trials adhere to the regulatory requirements
- Review of audit results with regards to safety, toxicity, protocol compliance and data integrity
- Review of safety issues of clinical trials participants
- Oversight and maintenance of the DSMP

The VICC DSMC convenes on a quarterly basis and additional ad-hoc meetings may be conducted to address urgent patient safety and data integrity issues which may be noted by the investigational team, internal auditors, or the DSMC. A quarterly summary of the DSMC's review of the serious adverse events is sent to the study PI and Vanderbilt IRB.

The DSMC also provides oversight of the internal audit function as part of the DSMP. This is a Vanderbilt Sponsored Investigator-Initiated Study that meets the VICC DSMP criteria as a Low Risk study. A Low Risk study will be audited annually. During each audit, 10% of the accrued patients since the previous audit with a minimum of 4 patients will be reviewed by the QA auditor.

During the scheduled audits, the QA auditor will review the patients selected for audit for the following:

- properly signed and dated informed consent
- patient eligibility
- correct treatment and treatment sequence
- evaluation of disease outcome/tumor response
- adverse event reporting
- drug accountability and proper storage/security
- general quality of data collected

A regulatory and pharmacy audit will also be conducted as needed. The outcome of the audit is first reviewed by a member of the VICC DSMC. If the DSMC member finds that the audit findings are problematic then the audit report is sent to the DSMC for a full committee review. The DSMC will then determine if the findings in the audit report require a response from the Principal Investigator. Upon review of submitted corrective action plans, the committee maintains the authority to approve the continuation of the study, increase the frequency of auditing, suspend accrual or terminate a protocol.

9.0 Study Withdrawal / Discontinuation. Subjects may be withdrawn from study participation at the discretion of the investigator or if the patient/family or attending physician requests that the subject be withdrawn. The reason and date of every withdrawal will be recorded. The Informed Consent Document will notify participants that their participation is voluntary, and they can tell the study staff at any time if they decide to stop participating. In addition, if they choose to withdraw their authorization for study staff to access protected health information (PHI) in the medical record, they may do so by notifying study staff in writing (the address is provided). If a participant chooses to no longer participate but does not notify study staff that they withdraw authorization for access to PHI, their medical record may be accessed to obtain outcomes and safety data. Data destruction will be overseen by the VCC for patients that withdraw from the study and want to have their data destroyed.

10.0 Statistical Considerations

10.1 Power analyses and sample size calculations. Previous studies have demonstrated a moderate effect (effect size ~0.4) of early palliative care on TOI, which is the primary outcome of the SCOPE trial. Assuming a type I error rate of 5% and a common standard deviation of 18.1 in the FACT-G TOI score in each group, 98 subjects in each group at 90 days (total N=196) would provide the study with at least 80% power to detect a change of 7.28 points (an effect size of 0.4) for TOI, the primary outcome of the SCOPE trial. Assuming 15% loss to follow-up at 90 days, enrolling 118 patients per group (total N=236) would provide this level of power. The study will not be powered to meet the secondary and exploratory outcomes.

The demographic and clinical characteristics of patients will be described using descriptive statistics. For continuous variables, median and interquartile range will be used while categorical variables will be described using frequency (percentage).

To examine the unadjusted effect of treatment on the primary end-point for the SCOPE trial, 90-day functional status as measured by the FACT-G TOI, we will use the Wilcoxon rank-sum test. In addition to unadjusted analyses, we will also perform multivariable regression to adjust for a priori-selected risk factors for outcomes, including age, frailty, cancer type, insurance status, education level, and degree of religious involvement. We will choose the type of multiple regression by carefully examining the distribution of the data. In the case of non-normally distributed outcomes, we will use a multivariable proportional odds regression model. To determine the unadjusted effect of early PCC on hospital length of stay, survival, and other time-to event outcomes, the cumulative incidence probability of these outcomes will be estimated via the Kaplan-Meier product limit method, and the log-rank test will be used to compare groups. Cox proportional hazards regression will be used to analyze the adjusted effect of PCC on time-to-event outcomes, with censoring as appropriate. To evaluate the unadjusted association between early PCC and receipt of intensive life-prolonging therapy in the last two weeks of life,

chi-squared tests will be used. A logistic regression model will be used for adjusted analysis to estimate the odds of receiving intensive life-prolonging therapy due to early PCC. Missing data will be imputed using a model-based imputation process. Non-linear effects of continuous variables will be fit using restricted cubic splines, and modern regression model building techniques will be used. All covariates included in the adjusted models will be selected a priori and the model complexity will be based on the general rule that a model must fit no more than $m/10$ parameters to allow for proper multivariable analysis and to be generalizable to future patients, where m is the effective sample size. Graphical techniques will be used to perform model diagnostics and evaluate assumptions. Multicollinearity will be assessed using variance inflation factors and in the event of highly collinear variables, principal component analysis will be used.

10.2 Missing Data. When data cannot be collected, we will impute missing variables via multiple imputation methods. Missing data are common due to deaths and loss to follow-up. While our team has a proven track record of achieving high follow-up we will carefully analyze whether particular baseline demographics are associated with missing evaluations of long-term testing.

10.3 Statistical Meetings. The VCC will work regularly with our statisticians at the ongoing weekly biostatistics meetings. Final analyses will occur during the last 6 months of the study period, when monitoring, quality checks, data lock, archiving and manuscript preparation will take place.

11.0 Privacy/Confidentiality Issues. Protected Health Information (PHI) will be kept confidential and shared with other investigators or regulatory bodies only when in accordance with relevant governmental and institutional policies. At no time will we reveal subject identities in any manner, whether in presentation, description or publication of the research for scientific purposes. All data obtained with subject or provider identifiers will be kept in locked file cabinets to ensure confidentiality, and all paper file contents will be shredded before disposal. All subjects will be assigned a unique study number for use in the computer database, and all electronic data will be kept in password-protected computer files to ensure confidentiality.

Most data will be collected from medical records or direct assessments and entered directly into the study database via electronic case report forms (eCRFs). Paper CRFs will be used for baseline cognitive impairment, quality of life, and follow-up neuropsychological battery (some may require copyrighted forms). Once collected on paper, data will be directly entered into the database. The study will utilize a centralized database located on Vanderbilt's secure REDCap database system.

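### The 80% power in section 10.1 matches a t-test; the Wilcoxon test named for the primary endpoint gives about 78 to 79% if scores are roughly normal

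*Combined protocol and SAP*

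**What the plan says.** All the sample size inputs stand in section 10.1. The calculation is introduced with "Assuming a type I error rate of 5% and a common standard deviation of 18.1 in the FACT-G TOI score in each group". It says that 98 patients per group at 90 days "would provide the study with at least 80% power to detect a change of 7.28 points (an effect size of 0.4) for TOI". Enrolment is then raised to 118 per group (236 in total): "Assuming 15% loss to follow-up at 90 days". The section names no test for this calculation and does not say whether the 5% is one- or two-sided.

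For the unadjusted treatment effect on 90-day TOI, the same section says "we will use the Wilcoxon rank-sum test". It adds multivariable regression on age, frailty, cancer type, insurance, education and religious involvement. Baseline TOI is not in that list, although Aim 1 and section 4.2.1 define the primary endpoint as the 90-day score with the baseline score controlled for. No analysis is labelled primary.

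On attrition, section 10.2 says "Missing data are common due to deaths and loss to follow-up" and plans multiple imputation. Section 7.2.2 evaluates outcomes among survivors. The documents give no 90-day death rate.

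**The concern.** A power statement should describe the test that will be run. Here the figure has no slack: 98 per group is just where a t-test reaches 80%. A rank-sum test on normal data is slightly less efficient than a t-test, so it falls below the claimed floor at the same sample size. A reader also cannot tell whether the 80% refers to the Wilcoxon test, to a t-test, or to an analysis adjusted for baseline, and these have different power. At stake is the accuracy of a stated design figure for the primary endpoint. The viability of the trial is not in question.

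**Working it through.** **Inputs (section 10.1).** Difference 7.28; SD 18.1; alpha 0.05, taken as two-sided because that reproduces the figure (one-sided gives about 88%); 98 evaluable per group; 118 enrolled per group; 15% loss. Allocation is 1:1 (section 6.1).

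**Step 1. Reproduce the plan's figure.**
- Standardised effect: d = 7.28 / 18.1 = 0.4022.
- Noncentrality: d × √(n/2) = 0.4022 × √49 = 2.815.
- Normal approximation: Φ(2.815 − 1.960) = Φ(0.855) = 80.4%.
- Noncentral t: 80.0% at 98 per group (required n = 98.005).

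The stated figure is therefore correct for a two-sided t-test.

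**Step 2. Same inputs, Wilcoxon test, normal data.** The asymptotic efficiency relative to the t-test is 3/π = 0.955, so 98 per group is worth 98 × 0.955 = 93.6.

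| Method | 98 per group | 100 per group |
|---|---|---|
| t-test, for comparison | 80.0% | 80.8% |
| Wilcoxon, 3/π with noncentral t | 78.1% | 79.0% |
| Wilcoxon, 3/π with normal approximation | 78.6% | 79.4% |
| Wilcoxon, Noether's formula | 77.5% | 78.3% |
| Wilcoxon, simulation (40,000 trials) | 78.1% | 78.8% |

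The 100 per group is what enrolment yields after the planned loss: 118 × 0.85 = 100.3.

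**Step 3. Size that would give 80% with Wilcoxon under normality.** 98.005 × π/3 = 102.6, so about 103 evaluable per group (simulated power 80.4%). At 15% loss this is 103 / 0.85 = 121.2, so 122 per group or 244 in total, against 236 planned.

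**Step 4. Dependence on the normality assumption.** Simulated Wilcoxon power at 98 per group with the same standardised shift and unit variance (20,000 trials each): normal 78%; mildly skewed (gamma, skewness 0.5) 80%; heavy-tailed (t with 5 degrees of freedom, rescaled) 87%. These shapes are assumptions; the documents do not describe the TOI distribution.

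**Step 5. Baseline-adjusted analysis.** Adjusting for a baseline score with correlation ρ divides the residual SD into the effect as d / √(1 − ρ²). At 98 per group under a normal model:
- ρ = 0.3: 0.4022 / 0.954 = 0.422, power about 84%.
- ρ = 0.5: 0.4022 / 0.866 = 0.464, power about 90%.

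The correlations are assumed; the documents give none.

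**Step 6. Attrition that 118 can absorb.** (118 − 98) / 118 = 20 / 118 = 16.9%. The plan's 98 evaluable per group holds if all causes of a missing 90-day score, deaths included, total at most about 17%.

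**The case against.** The strongest reply is that nothing was miscalculated. The figure reproduces, the plan never says it was computed for the Wilcoxon test, and the shortfall is 1.9 points at 98 per group and about 1 point at 100. It disappears if scores are mildly skewed or heavy-tailed, and the plan itself provides for non-normal outcomes. The endpoint is also defined with baseline controlled for, and an analysis of that kind would probably exceed 80%. All of this stands, and it makes the point minor. It does not settle it, because the only named test is unadjusted, baseline TOI is missing from the listed covariates, and nothing says which analysis the 80% describes.

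Three stronger readings are tempting, and the documents do not support them.

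- **Deaths lower the power further.** The 98 are patients at 90 days, and the 15% may already include deaths. No death rate is given, and missing values are to be imputed. Deaths cost power only if they come on top of the 15% and exceed about 2% of those enrolled.
- **Follow-up will be 80%.** Section 7.6 says earlier studies "consistently achieved over 80% follow-up during previous studies". That is a floor from past work. Section 7.3.1 sets a target above 85% for this trial, which agrees with the 15% allowance.
- **7.28 points is an error for 0.4 × 18.1 = 7.24.** The ratio 7.28 / 18.1 = 0.402 rounds to 0.4, and 7.28 is also 0.4 × 18.2, so a rounded SD would explain it. This is rounding.

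**Conclusion.** The point holds, as a minor one. The claim of at least 80% power is accurate for a two-sided two-sample t-test on the plan's inputs, and slightly too favourable for the one test that the plan names for the primary endpoint. For that test, power is about 78% at 98 per group and about 79% at the 100 expected after 15% loss. This rests on three things: two-sided alpha, roughly normal scores with a common SD of 18.1, and an analysis of evaluable patients only. That a t-test underlies the plan's figure is inferred from the exact match. A reader might infer that the trial is underpowered. The documents do not support this, since the gap is 1 to 2 points and either a non-normal score distribution or adjustment for baseline could close it.

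**What to change.** Keep 236 patients and revise the power paragraph in section 10.1.

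1. Name the test and the sidedness behind the figure.
2. Then choose one of two routes. (a) Keep the Wilcoxon test and restate its power as about 78 to 79% for 98 to 100 evaluable per group, assuming near-normal scores. (b) Make the baseline-adjusted analysis primary, in line with section 4.2.1, add baseline TOI to the model, and quote power with the assumed baseline correlation and its source.
3. State that 118 per group leaves 98 evaluable only if total attrition, deaths included, is at most 17%, and say whether the 15% counts deaths.

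The cost is one paragraph of wording. Under route (a) the stated power becomes 1 to 2 points less favourable. Route (b) also needs a change to the listed covariates and a defensible correlation.

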The Surgery for Cancer with Option of Palliative Care Expert (SCOPE) Trial is an investigation that will study the effect of a palliative care implementation during the preoperative, perioperative, and postoperative phase for older adults undergoing cancer surgery for selected (see inclusion criteria) abdominal malignancies. SCOPE will be a single-blind, single-institution randomized controlled trial of 236 patients. Intervention arm patients will receive a preoperative outpatient specialty palliative care consultation from a palliative care provider (physician or nurse practitioner) in addition to inpatient and outpatient palliative care follow-up postoperatively. Control arm patients will receive usual care with PCC available at the discretion of the primary treatment team (currently these patients rarely get PCC and usually only in the last weeks of life). **The central hypothesis of the SCOPE Trial is that preoperative, perioperative, and postoperative specialty PCC will improve patient functioning and quality of life while decreasing intensive life-prolonging therapy at EOL in patients undergoing resection of selected abdominal malignancies.**

Specific Aims

Aim 1: To determine whether preoperative, perioperative, and postoperative specialty palliative care consultation improves 90 day post-operative functional status. We hypothesize that PCC will improve physical and functional quality of life as measured by the Trial Outcome Index (TOI) of the FACT-G instrument in patients undergoing resection. The SCOPE Trial's primary end-point will be TOI at approximately 90 days postoperatively, controlling for baseline score. Secondary end-points will be QOL (FACT-G) at approximately 90 days and days alive at home during the first 90 days. Exploratory endpoints will be anxiety, and depression (PROMIS Anxiety-6 and Depression-6) and Karnofsky performance status at 90 days; satisfaction with hospital stay; and initiation of appropriate adjuvant therapy.

Aim 2: To determine whether preoperative, perioperative, and postoperative specialty palliative care consultation improves cancer survivorship. We hypothesize that PCC will improve the length and quality of life for patients undergoing resection. Secondary outcomes for

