4.2 Efficacy Endpoints

4.2.1 Primary Endpoint. The trial's primary endpoint will be score on the FACT-G TOI at 90 days post-operatively (controlling for baseline score).

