6.0 Enrollment/Randomization

6.1. Screening and Obtaining Informed Consent. Patients will be identified at their clinic visits to a surgeon to schedule a resection of an eligible malignancy. Study staff will determine eligibility. When an eligible patient is identified (i.e., inclusion criteria are met and no exclusion criteria are present), informed consent will be pursued. Additionally, the patient will identify a caregiver who will be the subject for caregiver evaluation and will be the contact person in later phases of the study if the patient is unable to respond for him or herself. In some cases, the main caregiver may change due to various circumstances and a new caregiver will be contacted. Patient will be randomized and assigned via randomization to the Intervention Group or the Control Group.

To maintain group balance among types of malignancy, a critical determinant of outcome, the treatment group allocation will be specified by stratified randomization. We will randomize patients meeting all eligibility requirements in a 1:1 ratio to early PCC or standard of care using a computer-generated randomization scheme using a permuted block design, stratified by type of cancer. The randomization scheme will be created by the trial's primary biostatistician and be directly uploaded into REDCap's randomization module. In rare cases some patients may be enrolled into trial but not randomized for uncontrollable reasons such as a surgery date is talked about with patient with the expectation that surgery may not occur due to lack of response to a therapy. Some surgeons have tight windows of time scheduling the patient a few days after a scan which gives little room to meet with patient to consent and complete pre-surgery interventions. It will be rare (<10% of patients enrolled) that a patient is consented without randomization but the study team wants the option to connect with these patients when it is most convenient for them. The goal is to have 236 randomized patients with the expectation that more than 236 patients may be enrolled/consented to get to a total of 236 patients randomized.

6.2 Blinding. The post-op assessments of patients will be completed by a masked outcome assessor who is not aware of randomization assignments of patients. The assessors will be trained to avoid discussing assignment during their interactions with subjects.

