7.0 Study Procedures

7.1 Enrollment. After informed consent is obtained, on the day of enrollment baseline demographic, clinical, and psychometric data will be collected on all consented subjects if feasible. If baseline information is not obtained on consent day, it will be completed as soon as possible and always before scheduled operation date.

The following procedure will be conducted:

A **baseline function assessment** form will ascertain important information about the patient's baseline functional status, including history of depression and anxiety. Quality of life will be measured.

7.2 Intervention Trial. The Intervention Trial Phase will comprise of the Pre-operative Phase, In-Patient Phase, and the Long-Term Follow-up Treatment Phase. Patients in the control group will receive routine care for their malignancy and can receive palliative care consultation at the discretion of their providers. Patients assigned to the intervention group will be immediately scheduled for a preoperative outpatient palliative care consultation by a physician or

nurse practitioner on the Vanderbilt palliative care team. This encounter will focus on advance care planning, helping the patient articulate goals of care, and addressing any symptoms the patient is experiencing. If the patient is unable to come for the scheduled in-person consultation, a provider will contact them by phone to provide a phone consultation. Intervention patients will be compensated with a \$50 gift card or check for coming to the pre-operative in person palliative care visit. Patients in the intervention group will also receive an inpatient palliative care consultation at least twice weekly during post-op hospitalization focusing on pain and symptom management and addressing any psychosocial distress around the operation. While inpatients, the palliative care team will follow these patients at the discretion of the palliative care provider.

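### The primary endpoint is 90-day TOI controlling for baseline, but neither analysis in section 10.1 names baseline TOI and neither is labelled primary

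*Combined protocol and SAP*

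**What the plan says.** The endpoint is defined twice, both times with baseline built in. Aim 1 (section 1.0) says the "primary end-point will be TOI at approximately 90 days postoperatively, controlling for baseline score". Section 4.2.1 gives it as "score on the FACT-G TOI at 90 days post-operatively (controlling for baseline score").

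Section 10.1 then describes two analyses of this endpoint:

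- For the unadjusted treatment effect, "we will use the Wilcoxon rank-sum test".
- In addition, a multivariable regression will "adjust for a priori-selected risk factors for outcomes, including age, frailty, cancer type, insurance status, education level, and degree of religious involvement". Its type is to be chosen after looking at the distribution of the data, with proportional odds if the outcome is not normal.

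Later in section 10.1: "All covariates included in the adjusted models will be selected a priori and the model complexity will be based on the general rule" of at most m/10 parameters, where m is the effective sample size.

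Two other sections bear on the repair. Section 7.1 says that "on the day of enrollment baseline demographic, clinical, and psychometric data will be collected on all consented subjects if feasible", and otherwise before the operation. Section 6.1 randomizes "using a permuted block design, stratified by type of cancer".

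**The concern.** A rank-sum test has no covariates, so the one test fully specified for the primary endpoint does not do what the endpoint definition asks. The regression could do it, but its six named covariates leave out the one that the definition requires. The word introducing the list leaves it open, so baseline TOI is unnamed rather than excluded. Even so, the plan wants every covariate fixed in advance, and this one is part of the endpoint.

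Two things are at stake. First, the plan does not say which result answers the primary question. There are at least two candidate p-values, and the type of one model is still to be chosen from the data. Second, if the analysis is run as listed, it forgoes the precision that a planned baseline measure offers.

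**Working it through.** **Inputs from section 10.1.** SD 18.1, difference 7.28 points, 98 evaluable per arm (196 in total), type I error 5%, power at least 80%, 15% loss, 118 enrolled per arm.

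**Assumptions.** The test is two-sided (sidedness is not stated; one-sided would give 77 per arm). SD 18.1 is the 90-day SD. The correlation r between baseline and 90-day TOI is not in the documents and is taken as 0.2 to 0.6.

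**1. The plan's own figure.** The effect size is d = 7.28/18.1 = 0.402. A two-sided, two-sample comparison gives n = 2(1.96 + 0.842)²/0.402² ≈ 98 per arm. Power at 98 is 80.0% by t-test (80.4% by the normal formula). Allowing for loss, 98/0.85 rounds up to 116, close to the stated 118. The sample size stands. It uses the raw SD, so it corresponds to an unadjusted comparison.

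**2. Unadjusted Wilcoxon.** For normal data its efficiency relative to the t-test is 3/π = 0.955. Power at 98 per arm is 78.1%, and about 103 per arm would be needed for 80%.

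**3. With baseline TOI in the model.** The residual SD is 18.1·√(1 − r²), so the standardized effect becomes d/√(1 − r²). The SE of the mean difference is 18.1·√(1 − r²)·√(2/98), and the 95% half-width is 1.96 times that. For proportional odds, the approximation applies the factor 3/π to the sample size. The simulated column used normal data cut into 12 ordered categories, with 2,500 runs per r.

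| r | Linear ANCOVA power | Proportional odds, approx. | Proportional odds, simulated | Half-width (points) |
|---|---|---|---|---|
| unadjusted | 80.0% (t-test) | 78.1% (Wilcoxon) | – | 5.07 |
| 0.2 | 81.6% | 79.8% | 78.8% | 4.97 |
| 0.3 | 83.6% | 81.8% | 81.5% | 4.83 |
| 0.4 | 86.4% | 84.8% | 84.2% | 4.64 |
| 0.5 | 89.9% | 88.5% | 87.9% | 4.39 |
| 0.6 | 93.8% | 92.8% | 92.7% | 4.05 |

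**4. How often the choice of analysis matters.** Trials were simulated with 98 per arm and normal data. At the planned effect, the Wilcoxon test and baseline-adjusted ANCOVA fall on opposite sides of p = 0.05 in about 7% of trials at r = 0.2 and 18% at r = 0.6. With no true effect, counting success on either gives about 6% to 8% false positives instead of 5%. The plan does not propose counting either, but it has no rule against it.

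**5. Room under the m/10 rule.** With m = 196, 19 parameters are allowed. Treatment takes 1, baseline TOI 1 (linear) or 2 (three-knot spline), and cancer type 7 if it has 8 levels. That number is an assumption borrowed from the eight operation categories in section 5.1, because section 6.1 gives none. The core model uses 9 to 10, leaving 9 to 10 for age, frailty, insurance, education and religious involvement.

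**The case against.** The strongest reply is that the protocol, read as a whole, already settles the adjustment. Baseline control is stated in advance in two places and the covariate list is open, so only a cross-reference and a label are missing. On that reading no precision is lost. This is fair as far as it goes, and the precision argument applies only if baseline TOI is in fact left out. But the reading makes the regression primary, and that is the less specified of the two analyses. Reading the Wilcoxon test as primary because it comes first contradicts the endpoint definition. Neither reading is free of a gap.

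A second reply is that the power comparison should start from the regression already planned, not from the unadjusted test. This trims the size. If the listed covariates explain 5%, 10% or 15% of the variance (an assumption), the planned linear model already has about 82%, 84% or 86% power. If baseline TOI is uncorrelated with those covariates, it still adds about 1.6 points at r = 0.2 and 12 to 13 points at r = 0.6. Any correlation with them would reduce that gain.

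Three smaller points also stand:

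- At r = 0.2 the simulated proportional-odds power (78.8%) is hardly above the Wilcoxon figure.
- With 118 enrolled and 15% loss, about 100 per arm remain, which puts the Wilcoxon test at about 79%.
- The parameter budget could be tight. Three-knot splines for age, frailty and religious involvement would use 6 of the remaining 9 to 10, leaving 3 to 4 for insurance and education.

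**Conclusion.** The concern holds and should be fixed. The documents define a baseline-controlled primary endpoint, fully specify only a test that cannot control for baseline, omit baseline TOI from the named regression covariates, and call neither analysis primary. The unadjusted test remains valid under randomization and 98 per arm is correct for it, so the trial's validity and size are not in question.

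The gain in power over the unadjusted t-test runs from under 2 points at r = 0.2 to about 14 points at r = 0.6 for a linear model. This rests on normal data, SD 18.1 at 90 days and an assumed r. The mismatch and the missing label follow from the text alone and need none of these assumptions.

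**What to change.** In section 10.1, name one primary analysis of 90-day TOI containing treatment, baseline TOI and the cancer-type randomization stratum. Choose ANCOVA or proportional odds and fix that choice before unblinded data are seen; the outcome distribution can be examined without arm labels if needed. List any further covariates, with their form and number of parameters, so that the total stays within 19 at m = 196. If the budget is short, drop spline terms or lesser covariates before baseline TOI or the stratum. Report the unadjusted Wilcoxon test as supportive.

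State also which assessment counts as baseline. Section 7.1 requires it before the operation but does not say before the preoperative palliative care visit, and a covariate measured after that visit could already reflect the intervention.

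The cost is wording only. Baseline psychometric and quality-of-life data are already planned and cancer type is recorded for randomization, so no patients, visits or instruments are added.
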